8.1.6. Death Events

Deaths occurring during the AE reporting period, regardless of attribution to DAY101 or combination partner will be recorded as a serious AE and expeditiously reported to the Sponsor. This includes death attributed to the progression of malignant disease.

When recording a death, the event or condition that caused or contributed to the fatal outcome should be recorded as the single medical condition on the Adverse Event eCRF and SAE report form, as applicable. If the cause of death is unknown and cannot be ascertained at the time of reporting, then “unexplained death” should be recorded on the Adverse Event eCRF and SAE reporting form, as applicable.

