
• Any abnormal laboratory test results (hematology, clinical chemistry, or urinalysis) or other safety assessments (e.g., electrocardiogram [ECG], radiological scans, vital signs measurements), including those that worsen from baseline, considered clinically significant in the medical and scientific judgment of the Investigator (i.e., not related to progression of underlying disease). In general, abnormal laboratory findings without clinical significance (based on the Investigator's judgment) are not to be recorded as AEs. However, abnormal laboratory findings that result in new or worsening clinical sequelae, require therapy, or adjustment in current therapy are considered AEs. Where applicable, clinical sequelae (not the laboratory abnormality) are to be recorded as the AE. If the clinically significant laboratory abnormality is a sign of a disease or syndrome (e.g., alkaline phosphatase and bilirubin $> 5 \times$ upper limit of normal [ULN] associated with cholecystitis), only the diagnosis (e.g., cholecystitis) needs to be recorded on the Adverse Event electronic Case Report Form (eCRF).• Exacerbation of a chronic or intermittent preexisting condition, including either an increase in frequency and/or intensity of the condition• New conditions detected or diagnosed after study intervention administration, even though it may have been present before the start of the study• Signs, symptoms, or the clinical sequelae of a suspected drug drug interaction• Signs, symptoms, or the clinical sequelae of a suspected overdose of either study intervention or a concomitant medication. Overdose per se will not be reported as an AE/serious adverse event (SAE) unless it is an intentional overdose taken with possible suicidal/self harming intent. Such overdoses should be reported regardless of sequelae.• Lack of efficacy will not be reported as an AE or SAE. Such instances will be captured in the efficacy assessments. Nonetheless, the signs, symptoms, and/or clinical sequelae resulting from lack of efficacy will be reported as AEs or SAEs if they fulfill the definition of an AE or SAE.• The term "disease progression" or "progressive disease" should not be reported as an AE, rather, report the specific malignancy as the AE term.

Non-Serious Adverse Events of Special Interest (Immediately Reportable to the Sponsor)

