Non-serious adverse events of special interest should be reported by the Investigator to the Sponsor immediately (ie, no more than 24 hours after learning of the event; see Section [8.1.4](#) for reporting instructions).

Adverse events of special interest for this study include the following:

1. Rhabdomyolysis
2. Ventricular Arrhythmias
3. Intra-tumoral hemorrhages
4. Secondary primary malignancies
5. Ocular toxicities

Events NOT Meeting the AE Definition

- Any clinically significant abnormal laboratory findings or other abnormal safety assessments that are associated with the underlying disease, unless judged by the Investigator to be more severe than expected for the patient's condition
- The disease/disorder being studied or expected progression, signs, or symptoms of the disease/disorder being studied, unless more severe than expected for the patient's condition
- Interventions for pretreatment conditions (e.g., elective cosmetic surgery) or medical procedures that were planned before study participation (e.g., port placement)
- Unplanned medical or surgical procedures (e.g., endoscopy, appendectomy). The condition that leads to the procedure is the AE
- Situations in which an untoward medical occurrence did not occur (social, logistical, and/or convenience admission to a hospital)
- Anticipated day-to-day fluctuations of preexisting disease(s) or condition(s) present or detected at the start of the study that do not worsen

Definition of SAE

If an event is not an AE per definition above, then it cannot be an SAE, even if serious conditions are met (e.g., hospitalization for signs/symptoms of the disease under study, death due to progression of disease).

An SAE is defined as any untoward medical occurrence that, at any dose:

a. Results in death

b. Is life-threatening

The term “life-threatening” in the definition of “serious” refers to an event in which the patient was at risk of death at the time of the event. It does not refer to an event that hypothetically might have caused death, if it were more severe.

c. Requires inpatient hospitalization or prolongation of existing hospitalization

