### **3.8.2. Summary of TEAEs**

The numbers and percentages of patients who experienced any TEAE, TRAEs, TEAEs with CTCAE grade 3 or higher, SAEs, treatment-related SAEs, TEAEs leading to treatment discontinuation, TEAEs leading to dose reduction, TEAEs leading to dose interruption, TEAEs leading to death, and all deaths will be presented by SOC and/or PT and highest CTCAE grade. An overall summary of the number and percentage of patients in each category will also be presented.

TEAEs with missing relationship will be presented in a by-patient listing.

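### Protocol 8.1.6 records a death from progression as an SAE while Appendix G names it as something that cannot be one, so the crude SAE and fatal-TEAE counts depend on which text a site follows

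*Protocol*

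**What the plan says.** Protocol 8.1.6 (Death Events): "Deaths occurring during the AE reporting period, regardless of attribution to DAY101 or combination partner will be recorded as a serious AE". The section goes on: "This includes death attributed to the progression of malignant disease".

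Protocol Appendix G deals with the same event in three places:

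- *Events Meeting the AE Definition*: sites should not use disease progression as a term; "rather, report the specific malignancy as the AE term".
- *Events NOT Meeting the AE Definition*: the list covers the disease under study "or expected progression, signs, or symptoms of the disease/disorder being studied, unless more severe than expected" for that patient.
- *Definition of SAE*: "If an event is not an AE per definition above, then it cannot be an SAE, even if serious conditions are met". The examples in brackets are "hospitalization for signs/symptoms of the disease under study, death due to progression of disease".

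Protocol 8.1 sends sites to Appendix G for how to collect, assess and report AEs. No text says whether 8.1.6 or Appendix G prevails.

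SAP 3.8.2 summarises SAEs, and "TEAEs leading to death, and all deaths will be presented by SOC and/or PT", with the highest CTCAE grade. SAP 3.3.3.1 defines a TEAE by timing alone: from first dose to 30 days after last dose, or to the start of subsequent therapy if that is earlier. SAP Section 4 lists only the efficacy analysis set as a departure from the protocol.

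**The concern.** One event is a named inclusion in one operative text and a named exclusion in another. An investigator whose patient dies of progression on treatment, or within 30 days of the last dose, can follow 8.1.6 and file a fatal SAE. The same investigator can follow the SAE definition in Appendix G and file none. The SAP counts what was entered.

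Safety is a secondary objective, and the sub-study is open-label without randomisation or a control arm. The absolute SAE and fatal-TEAE rates therefore have no concurrent background rate to be read against. If some sites file progression deaths and others do not, those rows combine tolerability and disease course in a proportion that a reader cannot recover from the row itself. There is also a conduct issue: SAEs must reach the sponsor within 24 hours, and a site cannot comply with both texts.

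**Working it through.** The documents give no figure on this point, so there is none to reproduce. The check is a comparison of texts followed by a bound.

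**Step 1. The texts side by side, for a death from progression in the reporting period**

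| Text | Result |
|---|---|
| Protocol 8.1.6 | Fatal SAE, whatever the attribution |
| Appendix G, SAE definition | Named example of what cannot be an SAE |
| Appendix G, events not meeting the AE definition | Not an AE, unless more severe than expected |
| Appendix G, events meeting the AE definition | Malignancy entered as the AE term |

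The second and third rows oppose the first. The fourth leans towards the first.

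**Step 2. Which outputs move**

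- *Move:* patients with any SAE, TEAEs leading to death, Grade 5 events, and to a lesser degree any-TEAE and Grade 3 or higher counts (SAP 3.8.2).
- *Do not move:* the all-deaths count (SAP 3.8.1 and 3.8.2; Protocol 7.3.2.1), OS, PFS, and the pausing criterion for a death related to study drug (Protocol 8.3).
- *Should move little:* treatment-related TEAEs and treatment-related SAEs, since a progression death would normally be judged not related under Protocol 8.5.

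**Step 3. The size**

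Inputs:
- N = patients in the Safety Analysis Set. Not given; the sample-size table is redacted.
- d = patients dying of progression inside the TEAE window. Not given.
- f = patients with any other fatal TEAE. Not given.

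Fatal-TEAE rate if every site follows 8.1.6: (f + d)/N.
Fatal-TEAE rate if every site follows the Appendix G exclusion and judges every such death as expected: f/N.
Difference: (f + d)/N − f/N = d/N.

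Mixed practice gives a value between the two. The any-SAE rate differs by at most d/N, because a patient who already has another SAE is counted either way.

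**Step 4. Illustration with assumed values** (f = 0; d/N of 5%, 10% and 20%; exact 95% intervals, shown only for scale because the SAP plans none for these rates)

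| N | Appendix G exclusion | 8.1.6, d/N = 5% | 8.1.6, d/N = 10% | 8.1.6, d/N = 20% |
|---|---|---|---|---|
| 20 | 0/20 (0 to 16.8%) | 1/20 (0.1 to 24.9%) | 2/20 (1.2 to 31.7%) | 4/20 (5.7 to 43.7%) |
| 40 | 0/40 (0 to 8.8%) | 2/40 (0.6 to 16.9%) | 4/40 (2.8 to 23.7%) | 8/40 (9.1 to 35.6%) |
| 60 | 0/60 (0 to 6.0%) | 3/60 (1.0 to 13.9%) | 6/60 (3.8 to 20.5%) | 12/60 (10.8 to 32.3%) |

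The shift in the rate is 5, 10 or 20 percentage points at every N, as d/N requires.

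**The case against.** The strongest reply is that the practical effect is small and largely visible.

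- Appendix G does not make every progression death a non-event. It excludes only expected progression, and its malignancy-term rule gives sites a way to enter the death as an AE. **This stands.** A reader might infer that a progression death simply disappears under Appendix G; the text does not support that. It does mean that Appendix G alone can yield either result, which adds to the ambiguity.
- No death is lost. Protocol 7.3.2.1 requires a listing of deaths with primary cause and days since last dose, and the SAP summarises and lists all deaths separately. **This stands**, and it limits the problem to the crude SAE and fatal-TEAE rows.
- Tolerability can be read from the treatment-related rows. **Largely true**, but those rows rest on investigator causality in an open-label study, and the crude rows will be reported beside them.
- The sponsor's safety physician gives SAEs a second assessment (Protocol 8.2.2), and monitors confirm proper SAE reporting (Protocol 9.3). **This helps in part.** The second assessment reaches only events that were filed, and monitors have the same two texts to work from.
- The window is short, and for unrelated events it closes earlier when new anticancer therapy starts. **This stands**; it keeps d down.
- The 102a sub-protocol and the EDC manual are not among the documents and may settle the matter. **This cannot be checked.**

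**Conclusion.** The contradiction is certain; its effect on the data is bounded but cannot be computed. Crude SAE, Grade 5 and fatal-TEAE counts can differ by up to d/N according to which text is followed. If d/N lay between 5% and 20%, which is an assumption, the fatal-TEAE rate would shift by 5 to 20 percentage points. The full shift needs every site to follow one text rather than the other and every progression death to be judged expected; mixed practice gives less.

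Two stronger readings are tempting. One is that the efficacy results or the stopping rules are compromised. They are not: OS, PFS and the count of all deaths do not use the SAE classification, and the pausing criteria in Protocol 8.3 require attribution to study drug. The other is that site practice did in fact vary. The documents show only that the texts permit it.

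The point deserves correction because it affects headline safety rows in a study without a control arm, and the data needed to resolve it are already required.

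**What to change.** **Master protocol.** Reconcile 8.1.6 with Appendix G so that one reporting rule applies. The edit must cover the example in *Definition of SAE*, the bullet on expected progression in *Events NOT Meeting the AE Definition*, and the malignancy-term instruction. Changing the example alone would leave the source of the exclusion in place. The master protocol also governs other sub-protocols, so the edit is useful although 102a has been terminated.

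**Sub-study 102a.** SAP 2.2.1 records that early termination was announced on 03NOV2023, so new wording cannot correct deaths already entered. Before database lock, check every death in the TEAE window against the AE and SAE records, using the primary cause of death required by Protocol 7.3.2.1, and apply one rule to all of them. State that rule in the SAP.

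**SAP 3.8.2.** Present SAEs and fatal TEAEs twice: including and excluding deaths attributed to progression. Keep both rows. The split depends on investigator-attributed cause in an open-label study, and a drug-related death called progression would drop out of the second row, so tolerability should not rest on that row alone.

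**Cost.** One wording amendment, which needs ethics approval before use (Protocol 9.1.2), one reconciliation step, and a few extra table rows. No new data collection is needed.

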8.2. Data Monitoring Committee (DMC)

An independent Data Monitoring Committee (DMC) will be established to oversee the safety aspects of the study and to render dose safety decisions as applicable based on sub-protocol (see Section 8.2.1).

8.2.1. Risk Management

An independent DMC will also be commissioned to monitor data on an ongoing basis to ensure the continuing safety of the subjects enrolled in the study and to review available efficacy data. The independent DMC will be composed of experts in the field of oncology, as well as biostatistics, and clinical trial conduct. Members of the independent DMC will not be associated with the conduct of the study, except in their role on the independent DMC. The Sponsor will also designate an independent biostatistical team not affiliated with the project to prepare and provide study data to the independent DMC. The independent DMC will meet periodically to review ongoing efficacy and safety data. Timing of the first independent DMC meeting will be enrollment driven, and subsequent meetings will occur approximately every 3 months (or longer based on patient accrual) to review safety across the DAY101-102 master study and sub-protocols. Complete details regarding the composition and governance of the independent DMC, independent DMC responsibilities, authorities, and procedures will be outlined in a separate independent DMC Charter. The independent DMC responsibilities, authorities, and procedures will be documented in a separate charter.

8.2.2 Continuous Review of Safety Data

The eCRF used for this study allows real-time tracking of safety data. Safety data review will be reviewed by the Sponsor or designee regularly, and safety signals or trends will be escalated to the DMC accordingly.

Serious adverse events will be reported within 24 hours to the Sponsor's safety team by email and be subject to a second assessment by the Sponsor's safety physician.

8.3. Stopping Rules

AEs and SAEs are expected to occur frequently in this study, based on the patient population being accrued and on the nature of the advanced malignancies under study. SAEs will serve as the basis for pausing or prematurely stopping the study. Unexpected SAEs that are assessed as related to DAY101 or combination partner will continuously be reviewed to determine any necessary pausing or stopping of the study. The study may be paused for enrollment if any patient experiences any of the following events:

- Life-threatening (Grade 4) toxicity attributable to DAY101 or combination partner that is unexpected and unmanageable (i.e., does not resolve to Grade 3 or lower within 7 days)
- Death related to DAY101 or combination partner

Review of these SAEs, and any decision to pause enrollment or terminate the study, will be determined by the Sponsor or at the recommendation of the DMC. Decisions to pause enrollment or terminate the study will be communicated promptly to Investigators,

IRBs/IECs, Institutional Biosafety Committees (if applicable), and appropriate regulatory authorities.

During any temporary enrollment hold, no new participants can be enrolled, nor can any newly enrolled participants start study intervention. Participants who have already started study intervention may continue treatment only if the benefit/risk assessment for the participant is judged to be positive by the Investigator in consultation with the Sponsor.

8.4. Grading and Intensity of Adverse Events

The Investigator will grade the severity of each AE using, when applicable, the NCI CTCAE, version 5. In the event of an AE for which no grading scale exists, the Investigator will classify the AE as mild, moderate, severe, life-threatening/debilitating, or fatal, as defined below.

Table 9: NCI CTCAE Definitions of Severity for Adverse Reactions

Toxicity	Grade / Details
Grade 1	Mild ; asymptomatic or mild symptoms; clinical or diagnostic observations only; no interventions required (an event that is usually transient in nature and generally not interfering with normal activities)
Grade 2	Moderate ; minimal, local, or noninvasive intervention indicated; some limitation of activities (an event that is sufficiently discomforting to interfere with normal activities)
Grade 3	Severe or medically significant but not immediately life-threatening ; hospitalization or prolongation of hospitalization required; disabling; limitation of patient's ability to care for him/herself (an event that is incapacitating with inability to work or do usual activity, or inability to work or perform normal daily activity)
Grade 4	Life-threatening consequences ; urgent intervention required (an event that puts the patient at immediate or potential risk of death, requires hospitalization, or which drastically impacts a patient's well-being)
Grade 5	Death related to adverse event (fatal)

Abbreviations: NCI CTCAE, National Cancer Institute-Common Terminology Criteria for Adverse Events.

8.5. Relationship to Study Drug

The Investigator is required to assess the causality/relationship between each AE and the study drug as not related or related and record the assessment on the source documents and in the CRF AE page. Medical judgment should be used to determine the likely relationship of the AE to the study drug considering all relevant factors including (but not limited to) relevant history, concomitant medical condition, and concomitant medications.

Determination should be based on assessment of temporal relationships, biologic plausibility, association (or lack of association) with underlying disease, and presence (or absence) of a more likely cause.

- **Related:** A causal relationship between medicinal product and an AE is at least a reasonable possibility. The AE cannot reasonably be explained by the patient's clinical state, concomitant medical condition or concomitant therapies, and a temporal relationship exists between the event onset and administration of the study drug.
- **Not Related:** It is plausible that the AE has an etiology other than the study drug (e.g., preexisting condition, underlying disease, concomitant medical condition, or concomitant medication).

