8. ADVERSE EVENTS

8.1. Adverse Events, Adverse Events of Special Interest, and Serious Adverse Events

Adverse events will be reported by the patient (or, when appropriate, by a caregiver, surrogate, or the patient's legally authorized representative).

The Investigator and any qualified designees are responsible for detecting, documenting, and recording events that meet the definition of an AE, AESI, or SAE and remain responsible for following up AEs that are serious, considered events of special interest, considered related to the study intervention or study procedures, or caused the patient to discontinue DAY101 or combination partner.

All AEs, whether reported by the patient or the patient's parent/legal guardian or noted by study personnel, will be recorded in the patient's medical record on the Adverse Event eCRF.

See Appendix G for instructions on collection, assessing, and reporting of AEs.

8.1.1. Time Period and Frequency for Collecting Adverse Event, Adverse Events of Special Interest, and Serious Adverse Event Information

Report all SAEs deemed related to protocol-mandated procedures from the signing of informed consent through to start of treatment with DAY101 or combination partner, whichever is administered first.

Report all AEs, AESIs, including SAEs, from the start of treatment until 30 days after the last dose of DAY101 or combination partner, whichever was administered last.

For patients who screen fail or are enrolled but do not receive study drug, the reporting period for SAEs ends 30 days after the last procedure (e.g., screening procedure).

Table 8: Summary of AE Collection Periods

Time Period	AE Collection
ICF signature to start of study drug	Protocol/procedure-related SAEs only
Start of study drug to 30 days after last study drug dose (DAY101, additional study treatment, whichever was administered last) ^a	All AEs, AESIs, and SAEs
Beyond 30 days after last study drug dose (DAY101, additional study treatment, whichever was administered last)	Any SAEs or AESIs related to study drug

Abbreviations: AE, adverse event; AESI, adverse event of special interest; ICF, informed consent form; SAE, serious adverse event.

^a See Section 8.1.3 for follow-up of AEs. If a patient begins a new anticancer therapy, the AE reporting period for non-SAEs and SAE/AESIs not related to study drug ends at the time the new treatment is started.

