- Examples of such events include invasive or malignant cancers, intensive treatment in an emergency room or at home for allergic bronchospasm, blood dyscrasias, or convulsions that do not result in hospitalization, or development of drug dependency or drug abuse.

Recording and Follow-up of AE, AESI, and/or SAE

AE, AESI and SAE Recording

- When an AE, AESI/SAE occurs, it is the responsibility of the Investigator to review all documentation (e.g., hospital progress notes, laboratory reports, and diagnostics reports) related to the event.
- The Investigator will then record all relevant AE, AESI /SAE information in the eCRF.
- It is not acceptable for the Investigator to send photocopies of the patient's medical records to the Sponsor in lieu of completion of the AE, AESI /SAE eCRF page.
- There may be instances when copies of medical records for certain cases are requested by Sponsor. In this case, all patient identifiers, with the exception of the patient number, will be redacted on the copies of the medical records before submission to Sponsor.
- **The Investigator will attempt to establish a diagnosis of the event based on signs, symptoms, and/or other clinical information.** Whenever possible, the diagnosis (not the individual signs/symptoms) will be documented as the AE, AESI /SAE (e.g., record liver failure or hepatitis rather than jaundice, asterixis, and elevated transaminases). In addition, AEs occurring secondary to other events (e.g., cascade events or clinical sequelae) should be identified by their primary cause (e.g., if diarrhea is known to have resulted in dehydration, then it is sufficient to record only diarrhea as an AE on the eCRF).

Assessment of Causality

- The Investigator and Sponsor is obligated to assess the relationship between study intervention (DAY101/additional therapies) and each occurrence of each AE, AESI /SAE.
- A “reasonable possibility” of a relationship conveys that there are facts, evidence, and/or arguments to suggest a causal relationship, rather than that a relationship cannot be ruled out.
- The Investigator will use clinical judgment to determine the relationship.
- Alternative causes, such as underlying disease(s), concomitant therapy, and other risk factors, as well as the temporal relationship of the event to study intervention administration, will be considered and investigated.

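### Section 8.5 applies inconsistent causality standards: an event with both a reasonable drug link and a plausible other cause becomes Not Related, so treatment-related rates, pause triggers and late reporting may be biased low

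*Protocol*

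**What the plan says.** Protocol Section 8.5 asks the investigator to label each AE Related or Not Related.

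- **Lead-in.** The judgment weighs timing, biologic plausibility, association with the underlying disease, and the "presence (or absence) of a more likely cause".
- **Related, first sentence.** "A causal relationship between medicinal product and an AE is at least a reasonable possibility".
- **Related, second sentence.** The event must also have no other reasonable explanation. The sentence names the patient's clinical state and then "concomitant medical condition or concomitant therapies, and a temporal relationship exists between the event onset and administration of the study drug", so the absence of alternatives and the timing are both required.
- **Not Related.** The whole test here is: "It is plausible that the AE has an etiology other than the study drug". The examples given are a preexisting condition, underlying disease, another medical condition or another medication.

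Appendix G (Assessment of Causality) says that a reasonable possibility "conveys that there are facts, evidence, and/or arguments to suggest a causal relationship, rather than that a relationship cannot be ruled out". There, alternative causes, "as well as the temporal relationship of the event to study intervention administration, will be considered and investigated".

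The label is used in three places:

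- **SAP 3.8.2** tabulates treatment-related TEAEs and treatment-related SAEs beside the all-cause categories.
- **Protocol 8.3** allows enrollment to be paused for "Life-threatening (Grade 4) toxicity attributable to DAY101 or combination partner that is unexpected and unmanageable", or for a death related to DAY101 or the combination partner.
- **Protocol 8.1.1, Table 8** limits collection more than 30 days after the last dose to "Any SAEs or AESIs related to study drug". Its footnote, repeated in 8.1.3, ends reporting of unrelated SAEs and AESIs as soon as new anticancer therapy starts.

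**The concern.** A two-way label should be exhaustive and exclusive, and should rest on one standard. Section 8.5 lets any plausible alternative override a reasonable drug link. Its lead-in asks for a comparison of causes, and Appendix G asks for evidence pointing to the drug. The same event can therefore be labelled differently depending on which text the investigator follows.

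The direction of error is one-sided. Section 8.3 itself expects frequent AEs and SAEs from the advanced malignancies under study, so another etiology will often be plausible. Following the wording of 8.5 then moves mixed-cause events out of the treatment-related category.

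Late events are the most exposed. Appendix G lists secondary primary malignancies as AESIs, and Section 6.13 names prior radiation among the risk factors for cutaneous squamous cell carcinoma. Such a carcinoma found after day 30 in a previously irradiated patient has a plausible other etiology. Under 8.5 it is Not Related, so Table 8 does not require its collection. No all-cause table can recover an event that was never collected.

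**Working it through.** The plan states no figure on this point, so there is nothing to reproduce. The check is logical, followed by an illustration that rests on an assumption.

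**Step 1: apply the definitions to every combination.** Three yes/no facts matter: whether a drug cause is reasonably possible, whether another cause is plausible, and whether there is a temporal link. I treat an event as reasonably explained by something else exactly when another cause is plausible, because the documents define neither term separately.

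| Drug cause reasonably possible | Other cause plausible | Temporal link | Meets Related (both sentences) | Meets Not Related |
|---|---|---|---|---|
| yes | no | yes | yes | no |
| yes | yes | yes | no | yes |
| yes | yes | no | no | yes |
| no | yes | yes or no | no | yes |
| yes | no | no | no | no |
| no | no | yes or no | no | no |

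Of the eight combinations, one is Related, four are Not Related, three meet neither definition, and none meets both.

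The second row is the one that matters. A mixed-cause event passes the first sentence of Related, fails the second, and satisfies Not Related. The last two rows are the gap: with no plausible other cause, an event lacking a temporal link or a reasonable drug link has no category.

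**Step 2: compare the four tests on a mixed-cause event with a temporal link.**

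- First sentence of Related: met.
- Section 8.5 lead-in: depends on which cause is more likely.
- Appendix G: met if facts, evidence or arguments point to the drug; alternatives are weighed and are not decisive.
- Section 8.5 definitions read whole: Not Related.

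**Step 3: illustrate the size.** Let m be the share of drug-caused events that also have a plausible other cause. The documents do not give m. Assume that all such events are labelled Not Related, that no event is wrongly labelled Related, and that each affected patient has one such event. Then the recorded related rate = true rate × (1 − m). For a true rate of 30%:

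- m = 10%: 30% × 0.90 = 27%
- m = 30%: 30% × 0.70 = 21%
- m = 50%: 30% × 0.50 = 15%

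For the pause triggers, assume that 8.3 is judged by the 8.5 label and that events are independent. The probability that at least one of k drug-caused trigger events is labelled Related is 1 − m^k:

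| m | k = 1 | k = 2 |
|---|---|---|
| 10% | 1 − 0.10 = 90% | 1 − 0.01 = 99% |
| 30% | 1 − 0.30 = 70% | 1 − 0.09 = 91% |
| 50% | 1 − 0.50 = 50% | 1 − 0.25 = 75% |

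At m = 0 there is no loss.

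**The case against.** The strongest reply is that this is a drafting inconsistency with little practical effect. Section 8.5 calls for medical judgment, and its lead-in and Appendix G both leave room to label a mixed-cause event Related.

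Several safeguards do not depend on the investigator's label:

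- All AEs, AESIs and SAEs are collected to 30 days after the last dose, unless new anticancer therapy starts.
- SAP 3.8.2 tabulates all-cause TEAEs, grade 3 or higher events, SAEs and deaths, and SAP 3.8.3 bases the AESI summaries on TEAEs.
- SAEs get a second assessment by the sponsor's safety physician (Protocol 8.2.2), and Appendix G makes the sponsor assess causality too.
- The IDMC evaluates all available safety data (SAP 2.3.4).
- The pause in 8.3 is discretionary, and the decision rests with the sponsor or follows a DMC recommendation.
- Under the SAP's treatment-emergent window (3.1.6, 3.3.3.1), late events would not enter the treatment-related tables in any case.

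All of this stands, and it limits the consequence. It does not remove it. The second assessment covers SAEs only, the IDMC cannot see late events that were not collected, and all-cause tables do not correct a treatment-related rate.

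A reader might also take the size from Protocol Table 4, where vomiting is 56% treatment-emergent against 24% related (32 points) and headache 40% against 12% (28 points). Those figures do not support that. They come from FIREFLY-1, a different study whose causality definition is not given here. A gap between the two columns is expected under any attribution rule and does not measure misclassification. In the same table rash (52%), hair color changes (68%) and fatigue (28%) show no gap at all.

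**Conclusion.** The inconsistency is real and is visible in the text. As written, Section 8.5 sends every mixed-cause event to Not Related and leaves some events without a category, contrary to its own lead-in and to Appendix G. Treatment-related AE and SAE rates, the pause triggers, and collection of SAEs and AESIs beyond 30 days or after new anticancer therapy may be biased low.

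Two stronger readings are not supported. A reader might infer that the categories overlap. They do so only if the first sentence of Related is read alone; with the second sentence there is no overlap, given that a plausible cause and a reasonable explanation are the same threshold. A reader might also infer that the three outputs are known to be biased low. The documents show a risk with a clear direction but not that investigators apply the wording literally, and they do not give its size. The 27%, 21% and 15% above are consequences of assumed values of m, not estimates for this trial.

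All-cause rates up to 30 days after the last dose, or to the start of new anticancer therapy, do not depend on the label.

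**What to change.** Use one standard in Section 8.5 and Appendix G:

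- **Related:** there is a reasonable possibility, supported by facts, evidence or arguments, that the study drug caused or contributed to the event.
- **Not Related:** there is no such reasonable possibility.

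Make temporality and alternative causes factors to weigh, not required conditions. Deleting only the clause on other explanations would not be enough: the temporal condition would remain in Related, and the categories would still not be exhaustive.

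Apply the change to continuing or future sub-protocols. For 102a, early termination was announced on 03NOV2023 and only the final analysis remains (SAP 2.2.1, 2.3.3), so new wording would not alter attributions already recorded. There, state the causality definition beside every treatment-related result and give the all-cause results primary weight.

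The cost is a protocol wording change and site retraining. More events will be classed as related, and any sub-protocol open at the amendment will hold labels made under two definitions, so its treatment-related summaries should identify the amendment date.
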